### 9.4 STATISTICAL ANALYSES

#### 9.4.1 ANALYSIS OF THE PRIMARY ENDPOINT(S)

Basic demographic tables will be generated for all depression ratings from baseline through follow-up periods, as well as general measures of central tendency for each variable (e.g., Mean, SD), measured categorically and continuously, and highlighted by measures of variability. For Feasibility, the following outcomes will be evaluated using descriptive statistics to identify: 1) the number of participants screened, eligible and enrolled; 2) at least 80% of all BAT and CBT sessions completed; and 3) 80% retention in all “outcome groups” (see attached figure in the IRB application).

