## 1 PROTOCOL SUMMARY

### 1.1 SYNOPSIS

Title:	Feasibility and acceptability of an adaptive treatment intervention for depression and engagement in HIV Care among Latinos living with HIV
Grant Number:	K01MH113475
Study Description:	This is the evaluation of the feasibility and acceptability of an adaptive intervention for depression and engagement in HIV care among Latinos living with HIV. The adaptive intervention is the sequencing of two low-risk behavioral interventions with text-messaging support. The focus of the study is on the sequencing of the interventions.
Objectives *:	Primary Objective: Feasibility of the intervention (i.e., execution of enrollment and intervention session completion rates). Secondary Objectives: Acceptability of the intervention (i.e., evaluation of engagement with intervention). Full details listed in the protocol.
Endpoints *:	Primary Endpoint: Half-way through active engagement with intervention (4 of 8 sessions completed) - this is the follow-up period dictating the sequencing decision. Secondary Endpoints: 12 weeks after enrollment - this is the final follow-up period.
Study Population:	A total of 45 Latino(a)/ Hispanic adult patients (18 or older) that are English or Spanish speaking, are living with HIV, report a mild level of depressive symptoms, and receive care at San Francisco General Hospital Ward 86.
Phase or Stage:	Not applicable
Description of Sites/Facilities Enrolling Participants:	Participants are recruited from Ward 86, at Zuckerberg San Francisco General Hospital in San Francisco, CA. This is a clinic setting with exam rooms, waiting room, and office space. Mission Hall is a research building at the Mission Bay Campus at U.C. San Francisco and includes private office and research study space.
Description of Study Intervention/Experimental Manipulation:	The interventions are behavioral activation therapy (BAT), cognitive-behavioral therapy (CBT) and text-messaging support. BAT is a 8-session one-on-one, in-person or video conferencing, intervention. CBT is an 11-session, one-on-one, in-person or video conferencing, intervention. Text-messaging support are one- and two-way SMS messages.
Study Duration *:	We expect a total of 12-months are needed to enroll 45 participants.
Participant Duration:	Participants are expected to be followed for 3 months.

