#### 4.3 JUSTIFICATION FOR INTERVENTION

The PI was a co-author of the first CBT intervention for Latinos living with HIV. In this study, there were improvements in self-reported depression and medication adherence, but a large portion of participants failed to complete all sessions, and weekly homework completion rates were also low. These limitations led to the current study, which focuses on starting individuals with a brief intervention first, and then supporting homework completion with text-message support.

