Conversely, participants randomized to the (A2) BAT & text-message support will receive an identical BAT program with the addition of one and two-way personalized text messages that will be delivered twice a week to facilitate engagement with the intervention activities.

**Text-Messages** - One-way messages will be sent as appointment and BAT adherence reminders (e.g., "Please remember to fill out your social activity planner?", while two-way text messages will be sent as "check-ins" with participants in the form of a mobile interventionist (e.g., "How is your activity planning going? If you need assistance, I can remind you of what activities you said you could do"). Participants will be asked to respond to these two way-text messages at their earliest convenience.

After three sessions of the five planned sessions have been completed, an assessment of the participants depression will be made using a cutoff score on the Patient Health Questionnaire-9 (PHQ-9), a self-reported rating scale for depression (this is called a "primary tailoring variable"). This primary tailoring variable will dictate the second sequence. Based on their PHQ-9 score, participants are coded as a "responder" or "non-responder;" a code that dictates whether their initial randomization assignment is 1) maintained, 2) augmented, or 3) switched to a second component (this is the second randomization and "adaptive" component).

**Participants who were randomized to BAT alone and were coded as "non-responders" will be randomized to:** 1. additionally receive text-message support, or 2. switched to receive CBT & text-message support. If switched to CBT & text-message support, participants will complete a total of eight intervention sessions that can be re-arranged to fit patient needs. CBT sessions will be scheduled once a week for 60 minutes (as described above, CBT integrates cognitive theory principles with behavioral theory principles, and thus, is more intensive). If participants randomized to BAT alone during their first stage of treatment and responded, they continue with maintenance of their BAT sessions.

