### 9.2 SAMPLE SIZE DETERMINATION

Daniel Almirall is a leading expert in SMART designs and developed a sample size estimation tool specifically for pilot SMARTs. First, we propose six treatment sequences and a minimum of four participants to receive them (called “outcome groups” in Figure 1). Second, one must estimate from the literature the percentage of participants who will not show a clinically meaningful response (i.e., “non-response rate”) to a treatment they will be initially randomized to. We used data from a non-inferiority trial of cognitive therapy versus a behavioral activation therapy in general population sample. This trial used clinician-administered diagnostic tools, self-report ratings, fidelity monitoring, and had all interventions delivered by psychologists and social workers. Under these rigorous conditions, 50-60% of participants with mild depression at baseline (range based on self-report and clinician ratings) did not achieve a 50% reduction in depressive symptoms at a 4-month follow-up. Similar results were found for participants with a higher severity of depression at baseline. This estimation tool yielded a total sample size of 45 participants if we observe a non-response rate of 50-60%, a fixed probability of 80% (suggested by Almirall), a minimum of four participants per “outcome group,” and a 10% attrition rate.

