#### 9.4.2 ANALYSIS OF THE SECONDARY ENDPOINT(S)

The Microsoft Excel file will have all participant appointment attendance records and responses to schedule text-messages, which were downloaded to determine acceptability as: 1) > 90% adherence to the BAT and CBT session schedule; 2) responsiveness to text-messages as: a) >80% of all two-way messages replied to during the set of blocked hours; b) >90% of participants reporting direct benefit from one-way text messages; 3) positive responses coded from post-intervention exit interview transcripts (to be determined at future date); 4) limited number of barriers to participation reported (to be determined at a future date).

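### The 80% session-completion mark pools BAT and CBT sessions, so it can be met with CBT completion well below 80%

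*Combined protocol and SAP*

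**What the plan says.** The synopsis (1.1) makes feasibility the primary objective and names session completion as part of it. Protocol 9.4.1 and the SAP section on the primary endpoint list three feasibility outcomes: counts screened, eligible and enrolled; "2) at least 80% of all BAT and CBT sessions completed"; and 80% retention in all outcome groups. No denominator, per-participant rule or per-component mark is given for the second. Section 9.3 says that no sub-analyses of feasibility or acceptability are planned.

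The first acceptability item in 9.4.2, 6.4 and the SAP is built the same way: "1) > 90% adherence to the BAT and CBT session schedule".

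Under 6.1.1, all participants start BAT, with or without text messages. Non-responders to BAT alone are re-randomised to "1. additionally receive text-message support, or 2. switched to receive CBT & text-message support". Non-responders to BAT with text messages get either a booster session or the same switch. CBT is therefore delivered only in B2 and B4. Section 4.3 explains that in the earlier CBT study "a large portion of participants failed to complete all sessions", and that this helped motivate the present design.

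**The concern.** Section 4.2 says that the pilot's outcomes are meant to justify the decision rules and inform the full-scale trial. Whether the switch to CBT can be delivered is a central part of that, and CBT is the component for which the protocol itself reports a completion problem. A pooled proportion weights each treatment by its number of sessions, and most sessions are BAT. Good BAT attendance can then offset poor CBT attendance, and the reported figure would not show it. The acceptability item on schedule adherence has the same weakness.

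**Working it through.** **The plan's own figure.** Section 9.2 states: "we propose six treatment sequences and a minimum of four participants to receive them". It gives 45 participants for 50-60% non-response, a probability of 80%, at least 4 per group and 10% attrition. Take equal arms and an even split of non-responders within arm. Each arm then needs at least 8 non-responders and at least 4 responders. The smallest N with probability at least 0.80 is 42 at 50% non-response, 38 at 55% and 36 at 60%. Dividing by 0.9 and rounding up gives 47, 43 and 40. The stated 45 is within 2 of the first two, so the design inputs can be used below.

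**Inputs.**
- N = 45, non-response q = 50-60% (9.2).
- BAT length L and sessions before the switch s: 5 and 3 (1.3, 6.1.1, 8.1), or 8 and 4 (1.1, 6.1.2, 8.1). The documents conflict.
- CBT length C: 8 (6.1.1) or 11 (1.1, 1.3). The documents conflict.
- Assumed: 1:1 allocation at both randomisations, equal non-response in both arms, and a denominator of sessions planned under each participant's own sequence.
- BAT completion b: not in the documents, so it is varied.

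**Formulas.** Number reaching CBT: c = N × q/2. BAT sessions: B = (N − c) × L + c × s. CBT sessions: K = c × C. The pooled mark is met when CBT completion is at least

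floor = [0.80 × (B + K) − b × B] / K = 0.80 − (b − 0.80) × B/K.

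Whenever BAT is above 80%, the floor for CBT is below 80%, and the shortfall is magnified by B/K.

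**5 BAT and 8 CBT sessions, 50% non-response.** c = 45 × 0.25 = 11.25. B = 33.75 × 5 + 11.25 × 3 = 202.5. K = 11.25 × 8 = 90, which is 31% of 292.5. With b = 0.95: 0.80 − 0.15 × 202.5/90 = 0.4625.

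**Same counts, 60% non-response.** c = 13.5, B = 31.5 × 5 + 13.5 × 3 = 198, K = 108 (35% of 306). With b = 0.95: 0.80 − 0.15 × 198/108 = 0.525.

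**All four combinations of session counts** (CBT floor at 50% to 60% non-response):

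| BAT / CBT sessions | B; K at 50% | B; K at 60% | BAT at 95% | BAT at 90% |
|---|---|---|---|---|
| 5 / 8 | 202.5; 90 | 198; 108 | 46-52.5% | 57.5-62% |
| 5 / 11 | 202.5; 123.75 | 198; 148.5 | 55.5-60% | 64-67% |
| 8 / 8 | 315; 90 | 306; 108 | 27.5-37.5% | 45-52% |
| 8 / 11 | 315; 123.75 | 306; 148.5 | 42-49% | 54.5-59% |

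With BAT at 85% the 5/8 floor is 69-71%. Removing 10% uniformly (N = 40.5) changes none of these rates. Counting booster sessions moves the rates by about one point.

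**If early dropouts count.** Suppose 4.5 people leave before re-randomisation with 5 planned BAT sessions each (22.5 sessions), and the other 40.5 have BAT at 95% (5/8 counts).
- At 50% non-response, B = 182.25 and K = 81 among those retained. The mark is 0.80 × 285.75 = 228.6, and retained BAT supplies 173.1. If dropouts completed half (11.25), the CBT floor is 44.2/81 = 55%. If they completed none, it is 55.5/81 = 68%.
- At 60%, B = 178.2 and K = 97.2. The mark is 0.80 × 297.9 = 238.3, and BAT supplies 169.3. The floors are 57.8/97.2 = 59% and 69.0/97.2 = 71%.

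**The >90% schedule mark**, treated as the same kind of proportion. With BAT at 100% and 5/8 counts, the CBT floor is (0.90 × 292.5 − 202.5)/90 = 67.5% at 50% non-response and (0.90 × 306 − 198)/108 = 72% at 60%.

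**The case against.** *Pooling is a reading.* The text could mean 80% of BAT sessions and 80% of CBT sessions. That is possible but not written. If it is intended, the fix below simply says so.

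*The size depends on inputs the documents do not supply.* This stands. A reader might infer that CBT can run at about half under any version of the plan. The documents do not support that. With 5/8 counts, a CBT floor of exactly 50% needs BAT completion of 93-96%. With 5/11 counts and 60% non-response, the floor is 53% even with perfect BAT. Counting early dropouts raises the 5/8 floor to about 55-71%.

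*Other criteria would catch it.* In part. Retention is set per outcome group, three missed visits with failed contact count as loss to follow-up (7.3), and serious non-compliance may lead to discontinuation (7.2). But 7.1 keeps participants who stop the intervention in all later assessments, so someone can abandon CBT and still be retained. A trial at exactly 80% overall would also be expected to miss the >90% schedule mark, but that mark is secondary and pooled.

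*No stated consequence.* This also stands. A reader might infer that meeting 80% declares the pilot feasible or carries B2 and B4 into a full trial. Section 9.4.1 lists three outcomes, all descriptive; 9.1 states no hypotheses; and no section ties this mark to advancing a sequence.

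*The earlier study.* Section 4.3 gives no completion rate, and this design adds a BAT-first sequence and text support. The history is a reason to look at CBT, not evidence that it will fail here.

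*Separate marks are imprecise.* With 11 people and 88 CBT sessions, three who attend none leave at most 64/88 = 73%. If each independently had a 15% chance of attending none (assumed) and the rest attended all, the chance of three or more is about 22%, although true completion is 85%. That argues against a hard gate, not for pooling.

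**Conclusion.** The point holds for the session-completion item on its plain reading. With BAT at 95%, the pooled 80% mark can be met with CBT at least 20 points lower than 80% under every combination of session counts in the protocol; the floor runs from about 27% to 60%. With BAT at 90% and 5/8 counts it is 57-62%. These figures rest on 1:1 second randomisation, equal non-response across arms, an assumed BAT rate and a denominator of planned sessions, and they are milder if dropouts' missed sessions are counted. Enrolment and per-group retention are separate outcomes and are not shown to pass. Attendance records would allow the split at reporting, but nothing in the plan commits to it.

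**What to change.** In 9.4.1 and the SAP, evaluate completion separately for BAT and for CBT, the latter among participants assigned to B2 or B4, each against the 80% mark. Give counts and a confidence interval that allows for clustering of sessions within participant. Keep the pooled figure as descriptive, and split the first acceptability item (6.4, 9.4.2, SAP) in the same way. Amend 9.3 so that it does not appear to rule this out.

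Reconcile the conflicting session counts and decision points (BAT 5 or 8, CBT 8 or 11, decision after 3 of 5 or 4 of 8). Then state the denominator: sessions planned under each participant's assigned sequence, including those who drop out.

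The cost is wording only, since 9.4.2 already has attendance recorded for every participant. The downside is precision. The CBT figure will rest on about 10-14 people (40.5 × 0.25 = 10.1 to 45 × 0.30 = 13.5), so it should be read with its interval and not used as a hard joint pass/fail gate.

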At the baseline interview, all participants will be asked to complete a locator form, which includes the listing of a current home address, phone number, and text or email information (if available), and preferences for how they would like to be contacted. The locator form also requests the names of three persons who they agree can be contact in the event they cannot be reached. The locator form also includes information we are allowed to relay over the phone or email (e.g., a participant may not mind that we state this is a call from the “Salud or Women’s Clinic” whereas another participant might prefer we state “UCSF”).

For subsequent appointments, each participant is sent a text-message and asked to confirm their next appointment. If they do not respond to the text-message within 24 hours, a second text-message is sent. Lastly, if the first two text-messages are not responded to, then a phone call is placed the following day. After three attempts, we make no additional outreach as to not burden the participant. Instead, we discuss communication efforts during the next face-to-face session. For participants randomized to the text-message tool, we have preliminary scheduled one-way text-message reminders to also be sent prior to their appointment. All participants have the option to reschedule if needed. If a participant misses a study appointment, they will be contacted to reschedule within 48 hours. A total of three attempts will be made to reschedule a missed appointment and we will make note of the reason for the missed appointment if provided. At each appointment a participant does attend, we will review their residence and contact information to ensure it is up to date and resolve any issues regarding future work or travel schedules should they arise. Additionally, all patients will have a monthly check-in call to verify their current home address and information and answer any questions about their participation. Given this comprehensive approach, we anticipate at least an 90% retention rate and have oversampled to ensure we have enough participants. All participants will be reimbursed with \$30 per session to cover all costs related to travel, and effort. We feel this reimbursement amount is not coercive and is necessary when adjusting for the high cost of living in the San Francisco Bay Area of California.

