### 7.3 LOST TO FOLLOW-UP

A participant will be considered lost to follow-up if he or she fails to return for 3 scheduled visits and study staff are unable to contact the participant after at least 3 attempts.

The following actions must be taken if a participant fails to return to the clinic for a required study visit:

- The site will attempt to contact the participant, reschedule the missed visit within 1 week, counsel the participant on the importance of maintaining the assigned visit schedule and ascertain if the participant wishes to and/or should continue in the study.
- Before a participant is deemed lost to follow-up, the investigator or designee will make every effort to regain contact with the participant (where possible, 3 text-messages and 2 telephone calls and, if necessary, a certified letter to the participant's last known mailing address or local equivalent methods). These contact attempts will be documented in the participant's medical record or study file.
- Should the participant continue to be unreachable, he or she will be considered to have withdrawn from the study with a primary reason of lost to follow-up.

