## 8 STUDY ASSESSMENTS AND PROCEDURES

### 8.1 ENDPOINT AND OTHER NON-SAFETY ASSESSMENTS

The focus of this study is on the feasibility of carrying out the assessment of a primary tailoring variable (PTV). A PTV is the cutoff score to decide whether a participant showed a clinically meaningful response to BAT or BAT & mHealth at a 1-month follow-up point. The preliminary cutoff score for the pilot SMART is defined as a decrease in a PHQ-9 score from the "moderate" to "mild" (or below) depression symptom severity category after 4 weeks (or after 4 of 8 sessions of BAT). The rationale for the follow-up period is to identify early who is a "responder" or "non-responder" to a 1st-stage treatment. The "responder/non-responder" decision is used to decide whether, when, and how to adapt a 1st-stage treatment. The follow-up point is the mid-way point of the brief intervention, that is, after 3 of 5 BAT sessions are complete. This cutoff score is supported by a randomized placebo-controlled trial that showed BAT to be associated with reduced depression more per week than a cognitive therapy on a self-rating scale. The same depression rating is done at the final follow-up period at the end of the final intervention session.

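### The 80% retention mark is set within six sequences that form only mid-treatment, so earlier losses fall outside it and groups of about six people can decide whether it is met

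*Combined protocol and SAP*

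**What the plan says.** Protocol 9.4.1 and the SAP (Analysis of the Primary Endpoint(s)) list three feasibility outcomes to be described. The third is "80% retention in all “outcome groups". Neither place gives a denominator, a date or a definition of retained. Both point to a figure that is not in the public text.

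Section 9.2 identifies the outcome groups: "we propose six treatment sequences and a minimum of four participants to receive them". Sections 6.1.1 and 6.1.2 give the six: responders in each first-stage arm, and two re-randomised options for non-responders in each arm. Membership depends on the responder code from the mid-treatment PHQ-9, "a code that dictates whether their initial randomization assignment is 1) maintained, 2) augmented, or 3) switched to a second component".

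On expected loss, section 9.2 allows for 45 participants "and a 10% attrition rate", and section 5.5 says "we anticipate at least an 90% retention rate and have oversampled to ensure we have enough participants".

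On timing:
- Section 5.5, under Retention, speaks of a three-month follow-up. The synopsis (1.1) gives 12 weeks as the final follow-up, under secondary endpoints. The schedule (1.3) has one final visit, at Day 84.
- The synopsis places the primary endpoint half-way through the intervention.
- Section 8.1 says "The same depression rating is done at the final follow-up period at the end of the final intervention session".

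On status, section 7.1 keeps people who stop the intervention in later assessments. Section 7.3 calls a participant lost who "fails to return for 3 scheduled visits and study staff are unable to contact the participant after at least 3 attempts". Neither section is linked to the 80% mark.

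**The concern.** A retention figure for a pilot should normally start from everyone randomised. Here the denominator is built from groups that do not exist until part-way through treatment, so loss between first randomisation and the decision point is not counted in any of them. That is loss that a full-scale trial would have to plan for, and section 4.2 says that the pilot informs such a trial.

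The mark is also applied to very small groups. A group of 4 can lose nobody and still reach 80%, groups of 5-9 can lose one person, and groups of 10-12 can lose two. A mark that all six must meet can fail because of two people in one sequence while overall retention is as good as planned.

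Because 9.4.1 names no assessment time and no rule for who is retained, two analysts with the same data could report different results.

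**Working it through.** **Inputs from the documents.** N = 45, six groups, at least 4 per group, 80% probability, 50-60% non-response and 10% attrition (9.2); at least 90% retention (5.5); final visit at Day 84 (1.3). The decision point is the Day 14 column in 1.3 but "after 4 weeks (or after 4 of 8 sessions of BAT") in 8.1, so both Day 14 and Day 28 are used.

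**Assumptions.** First-stage arms of 22 and 23; non-responders split evenly between their two options; losses independent between people. Constant dropout, where used, means a constant hazard over 84 days.

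**The plan's own figure.** Take the smallest N that gives at least 80% probability of 4 or more people in all six groups, and divide by 0.90.
- 50% non-response: 42/0.90, or 47.
- 55%: 38/0.90, or 43.
- 60%: 36/0.90 = 40.

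The stated 45 lies inside this range. The sample size is not in question.

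**Expected group sizes at N = 45** (22.5 per arm, before any early loss).
- Responder groups: 22.5 × 0.50 = 11.25 down to 22.5 × 0.40 = 9.0.
- Non-responder groups: 22.5 × 0.50 / 2 = 5.6 up to 22.5 × 0.60 / 2 = 6.75.

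**What leaving out early losses does to the pooled figure.** Let e be the proportion lost before the decision and r the retention after it, with (1 − e) × r = 0.90.
- Day 14: e = 1 − 0.90^(14/84) = 0.017, so r = 0.916, which is 1.6 points above 0.90.
- Day 28: e = 1 − 0.90^(28/84) = 0.035, so r = 0.932, which is 3.2 points above.
- No early loss: 0 points. All loss early: r = 1.00, which is 10 points above.

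**Each-group mark, one worked case.** Take sizes 9, 7, 7, 9, 7, 6 with 90% retention in each. A group of 6 meets the mark with probability 0.90^6 + 6 × 0.10 × 0.90^5 = 0.886. By the same sum, a group of 7 gives 0.850 and a group of 9 gives 0.775. All six meet it with probability 0.775² × 0.850³ × 0.886 = 0.33.

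**Each-group mark with random group sizes.** Overall retention is 90%. Ranges cover non-response of 50%, 55% and 60%.

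| Share of loss before the decision | At least one of six groups below 80% |
|---|---|
| None | 60-61% |
| Constant dropout, decision at Day 14 | 49-50% |
| Constant dropout, decision at Day 28 | 38-40% |
| Half | 27-30% |
| Three-quarters | 10-14% |
| All | 0% |

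**Comparators at 90% retention.** Fewer than 36 of 45 randomised kept: 1.2%. Pooled post-decision figure below 80%: 1.2% or less.

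**Same data, two readings.** If one group of 7 loses two people and nobody else is lost, that group is at 5/7 = 71% and misses. The pooled figure is 43/45 = 95.6% and passes.

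**False reassurance.** The chance that the mark is met while fewer than 36 of 45 are kept is 1.2% or less at planned retention, on either reading. Illustration only: if true retention were 75% with constant dropout, the pooled post-decision figure would reach 80% in 43% (Day 14) or 69% (Day 28) of trials, against 28% for 36 of 45.

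**Timing.** The half-way point cannot serve for this outcome. The groups are only forming then, so retention within them would be about 100% by construction. The end of the final session differs by sequence: in the 1.3 grid it falls by Day 35 for behavioral activation with the booster and by Day 70 for cognitive-behavioral therapy. Only Day 84 is common to all sequences.

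**The case against.** The strongest reply is that this is a descriptive pilot with no hypothesis and no decision attached to the mark. Early loss is also partly visible elsewhere. Outcome 1 in 9.4.1 reports the number enrolled, so early loss can be found by subtraction; 7.2 records reasons for withdrawal; and under 7.1 some people who stop early are still assessed and could still be coded. The missing figure might also assign early losses to a group. All of this stands and limits the priority. It does not make the stated mark count those who leave before coding and are not assessed.

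On timing, a reader might infer that the plan fixes no follow-up time. The documents do not support that: 1.1, 1.3 and the Retention text in 5.5 agree on about three months. The gap is that 9.4.1 does not refer to it, and that the half-way label in 1.1 and the end-of-session wording in 8.1 point elsewhere. Nor does 7.3 clearly exclude someone who misses only the final visit, because its action list starts with any missed required visit and ends in withdrawal if the person stays unreachable. The link to *retained* is unstated rather than contradictory.

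The ambiguity between each group and pooled is thin, since *in all* reads most naturally as each. A sequencing pilot also has a fair reason to want a group-level mark: if one group of six lost five people and nobody else were lost, pooled retention would still be 40/45 = 89%. Dropping any group-level mark is therefore partly a preference.

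**Conclusion.** The concern holds, with modest priority. As worded, the mark leaves out most losses before the responder code, so retention pooled over the groups is at or above retention among all randomised. The excess is 1.6 to 3.2 points at planned retention under constant dropout, and 0 to 10 points at the extremes. On its natural each-group reading the mark is missed in about 38-50% of trials that retain 90% as planned with constant dropout (0-61% over all dropout timings), against about 1% for 36 of 45.

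Two stronger readings should not be drawn. One is that every reported retention figure is inflated. That is true only of the pooled figure: in the same model with constant dropout, the lowest of the six group figures falls below all-randomised retention in about 93-98% of trials. The other is that the trial is likely to declare good retention wrongly. At planned retention that chance is 1.2% or less, and the 75% illustration lies outside the plan's own expectation.

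The result rests on the visible text without the figure, an even second-stage split and the stated dropout patterns. The direction of the pooled excess follows from the definition. The miss rates depend strongly on when people leave, which the documents do not say.

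**What to change.** In protocol 9.4.1 and the SAP:

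1. Define retention as participants with the final assessment, at one fixed time for all sequences, divided by all participants randomised at stage 1. Include those lost before the decision point and any who were replaced under 7.2, so the denominator may exceed 45. Apply the 80% benchmark to this figure and give an exact 95% confidence interval (for 36/45, 0.65 to 0.90).
2. For each of the six sequences, report the number retained over the number entering, and name any below 80% with the recorded reasons for loss. If the sponsor keeps a group-level mark, say that it applies to each group and state how often groups of this size would miss it at 90% retention.
3. Report the number lost before the decision point in each first-stage arm.
4. Reconcile the final-assessment timing in 1.1, 1.3, 5.5 and 8.1, and state how *retained* relates to people who stop the intervention but stay in assessments (7.1) and to loss to follow-up (7.3). The differing statements of the decision point in 1.1, 1.3, 6.1.1, 6.1.2 and 8.1 must be reconciled as well.

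The cost is wording only. The headline figure may be slightly lower because early losses count, and a group-level pass mark is replaced or qualified.
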